The primary analysis of primary efficacy variable 2 to address the primary objective will be based on the following estimand:

- Population: Defined through appropriate inclusion/exclusion criteria to reflect the targeted population and if a participant was not statin intolerant at the beginning of the trial
- Variable: Discontinuation of statin therapy (yes, no) [The primary analysis time point is at Day 330.]
- Treatment: "Inclisiran first" implementation strategy or usual care
- Remaining intercurrent events: 1. Potential use of inclisiran by participants in the usual care group. This intercurrent event will be ignored in the analysis, as the design of the trial allows for participants in the usual care group to potentially use inclisiran. 2. Discontinuation of study treatment. This intercurrent event will be ignored in the analysis.
- Summary measure: Treatment difference ("inclisiran first" implementation strategy – usual care) in the proportion of participants who discontinue statin therapy

The null hypothesis is that the difference ("inclisiran first" implementation strategy – usual care) in the proportion of participants who discontinue statin therapy at Day 330 is at least 0.15 (non-inferiority margin). The alternative hypothesis is that the difference ("inclisiran first" implementation strategy – usual care) in the proportion of participants who discontinue statin therapy at Day 330 is less than 0.15.

For primary efficacy variable 2, a one-sided 98.75% confidence interval for treatment difference ("inclisiran first" implementation strategy – usual care) in the proportion of participants who discontinued statin therapy at Day 330 will be computed using the normal approximation to the binomial distribution. Non-inferiority of the "inclisiran first" implementation strategy to usual care will be declared if the upper limit of the confidence interval does not exceed the non-inferiority margin of 0.15.

The primary analysis of both primary efficacy variables will be based on the Full Analysis Set.

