Responsibilities of principal investigator / routine care physician: Study visits will be done by the PI while routine care is performed by the participant's own treating physician. Communication and coordination between the PI and treating physician is allowed. However, PIs are asked to refrain from influencing treatment decisions that are usually made by the treating physician to maximize external generalizability (i.e., the influence of study participation on routine care should be as limited as possible). The PI and treating physician can be from the same practice.

Open-label: The study will be performed as an open-label study to mimic routine care decision-making, following from the primary objective of the study. For example, if the study would have been performed as a double-blind placebo-controlled study, it would not be possible to study the effect of inclisiran treatment on statin discontinuation as participants and investigators would not be aware of treatment allocation.

[figure not shown]
Duration of study period: The study is designed as a one-year trial (a total of three inclisiran doses). A follow-up duration of one year enables: 1) observation of the steady-state LDL-C lowering effect of inclisiran, 2) observation of a meaningful difference in statin discontinuations, should such a difference exist, and 3) assessment of variables that likely require longer-term treatment to observe meaningful treatment differences, such as patient reported outcomes.

Choice of non-inferiority margin for discontinuation of statin therapy: The sample size of the trial is partially based on the co-primary efficacy variable of discontinuation of statin therapy. The non-inferiority margin of 0.15 in the proportion of participants who discontinue statin therapy by Day 330 was chosen to reflect a clinically meaningful difference in statin discontinuation rates between the groups, while considering statin discontinuation rates described in other studies (Khunti et al 2018).

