2.2.1 Subgroup of interest

Subgroup analyses of the two primary efficacy variables and the secondary endpoint of absolute change from baseline in LDL-C will be performed for the following subgroups (note that results for a subgroup category will only be presented if the total across both treatment groups within the category is at least 10 participants):

- Background lipid-lowering therapy at baseline: Yes, No
- Medical history of statin intolerance: Yes, No (from medical history statin intolerance CRF page; do not use this subgroup for the co-primary efficacy endpoint discontinuation of statin therapy)
- Baseline statin intensity: High, Moderate or Low, None
- Age: <65 years, ≥ 65 years
- Baseline LDL-C: ≤100 and > 100 mg/dL; median; and then by quartiles
- Most recent ASCVD event: <1 year, ≥ 1 year (from targeted medical history CRF page, see below for more details)
- Diabetes at baseline: Yes, No (from targeted medical history CRF page)
- Renal impairment by eGFR categories at baseline: <15, ≥15 to <30, ≥30 to <60, ≥60 to <90, or ≥90 mL/min/1.73m²
- Sex: Male, Female
- Race: White, Non-White/Multiple (unknown will be excluded from subgroup analyses)
- Ethnicity: Hispanic or Latino, Not Hispanic or Latino (unknown or not reported will be excluded from subgroup analyses)
- [REDACTED]
- Coronary heart disease (CHD): Yes, No (from targeted medical history CRF page)
- Peripheral artery disease (PAD): Yes, No (from targeted medical history CRF page)
- Cerebrovascular disease (CVD): Yes, No (from targeted medical history CRF page)
- Polyvascular disease (>1 of CHD, PAD, or CVD): Yes, No (from targeted medical history CRF page)
- [REDACTED]

Most recent ASCVD event (<1 year, ≥ 1 year) is derived from data recorded on the “Medical History Targeted” form. The derivation is based on the timing of the most recent percutaneous coronary intervention, myocardial infarction, cardiovascular arterial bypass graft, or ischemic stroke. If a participant has multiple events with different timings, the earlier (<1 year) timing will be utilized. Participants without events are excluded from the subgroup.

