2.5.1 Primary endpoint(s)

The primary efficacy variables are the following:

1. Percent change from baseline in LDL-C
2. Discontinuation of statin therapy (i.e., no statin use \geq 30 days before the end-of-study visit) (yes, no)

The primary analysis time point for both primary efficacy variables is at Day 330.

The following provides additional details on the derivation of primary efficacy variable 2.

If a participant is considered a study completer and has a non-missing visit date for the nominal Day 330 visit recorded, a statin assessment date (to assess if the participant was taking statins at this point in time) will be calculated by subtracting 30 days from the Day 330 visit date (e.g., study Day 300 if the participant completes on study Day 330). The statin assessment date will be compared to the maximum statin end date of all statin medications taken by the participant. If the last statin is recorded as ongoing at study end date, the maximum statin end date will be set to the study end date.

- If the participant was on a statin on or after this statin assessment day (maximum statin end date \geq statin assessment date), the participant will be considered as discontinued statin = 'no.'
- If the participant was not on a statin on and after this statin assessment day (maximum statin end date $<$ statin assessment date), or they were a completer who did not have a Day 330 visit, the participant will be considered as discontinued statin = 'yes.'

All early termination participants will be considered to not be on a statin for this endpoint (the participant will be considered as discontinued statin = 'yes').

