For primary efficacy variable 2, a one-sided 98.75% confidence interval for treatment difference ("inclisiran first" implementation strategy – usual care) in the proportion of participants who discontinued statin therapy at Day 330 will be computed using the normal approximation to the binomial distribution. Non-inferiority of the "inclisiran first" implementation strategy to usual care will be declared if the upper limit of the confidence interval does not exceed the non-inferiority margin of 0.15. The difference in proportions and associated two-sided 97.5% confidence interval will also be provided.

The primary analysis of primary efficacy variable 2 will be based on the FAS excluding participants who had medical history of statin intolerance. The primary analysis of this variable will be repeated for the Per-Protocol Set and Restricted Set 2.

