For primary efficacy variable 2, i.e., discontinuation of statin therapy (yes, no), a z-test for a non-inferiority test of two proportions, an allocation ratio of 1:1, and a one-sided significance level of 0.0125 were used in the calculation of sample size. Table 3-2 considers total sample sizes for 0.20 and 0.25 as the true proportions of participants who discontinue statin therapy in each treatment group, and non-inferiority margins of 0.10 and 0.15 for the "inclisiran first" implementation group to be no worse than the usual care group (nQuery Version 8.4.1.0). From Table 3-2, a true proportion of 0.20 for participants who discontinue statin therapy in each treatment group by Day 330, a non-inferiority margin of 0.15, and a power of 0.90 were chosen to provide a total sample size of 354 participants.

Table 3-2 Sample Size Calculations for Statin Statin Therapy Discontinuation

Proportion in usual care group	Non-inferiority margin	Power = 0.85	Power = 0.90
0.20	0.10	688	796
0.20	0.15	306	354
0.25	0.10	806	932
0.25	0.15	360	414

Based on the sample size calculations in Table 3-1 and Table 3-2, a total sample size of 354 together with a loss to follow-up rate of 10% at Day 330 and a statin intolerance rate at baseline of 10% (i.e., a total of 20% due to loss to follow-up and statin intolerance at baseline) require

approximately 444 participants (222 participants per treatment group) to be randomized. This will also allow examination of subgroups with reasonable sample sizes.

4 Change to protocol specified analyses

Changes from Protocol version 01 (amended protocol) include the following:

1. Protocol Section 12.4.2 states that an unstructured working correlation matrix will be assumed for the MMRM. An unstructured covariance matrix will be used instead.
2. The protocol uses Day 0 as the first inclisiran dose day. In order to aid in counting of dosing days the first dose day will be referred to as Day 1.

Changes from Protocol version 02 (amended protocol) include the following:

3. Protocol Section 12 notes that the interquartile range will be provided. In order to streamline the tables this statistic was removed.
4. Protocol Section 12.2 notes that relevant medical histories and current medical conditions at baseline would be summarized using the Safety Set, the FAS was used instead.

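### The analysis set for statin discontinuation does not require a statin at baseline, so a non-user who never starts one is scored as having discontinued

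*SAP*

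**What the plan says.** SAP 1.1 calls this the "co-primary efficacy variable of discontinuation of statin therapy". It is tested for non-inferiority against a margin of 0.15, using "a one-sided 98.75% confidence interval for treatment difference" (SAP 2.5.2). The objective in both documents concerns background statin therapy.

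The population is set by intolerance alone. Protocol 12.4.2 admits a participant "if a participant was not statin intolerant at the beginning of the trial". SAP 2.5.2 uses the "FAS excluding participants who had medical history of statin intolerance". Neither adds a condition on statin use at baseline.

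The scoring rule in SAP 2.5.1 takes the Day 330 visit date minus 30 days as the assessment date. "If the participant was not on a statin on and after this statin assessment day", the outcome is 'yes'. Prior use is not asked for. SAP 2.5.4 adds that anyone whose statin use at the end of study cannot be ascertained is taken to have discontinued.

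SAP 2.2.1 lists subgroups for both primary variables and for absolute LDL-C change. One is "Baseline statin intensity: High, Moderate or Low, None". Only the intolerance-history subgroup is barred for the discontinuation endpoint.

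**The concern.** Only a participant who takes a statin at baseline can stop it. Someone with no intolerance history and no statin on Day 1 nevertheless stays in the analysed set. If that person never starts a statin, there is no statin end date to compare with the assessment date. The wording of the rule and the default for unascertained status both lead to 'yes'.

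Such a 'yes' carries no information on whether the inclisiran-first strategy leads people to stop their statin. In a superiority test, equal noise in both arms mainly costs power. In a non-inferiority test it also moves the observed difference towards zero, so a true excess at the margin is more likely to pass.

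**Working it through.** **Inputs from the documents (SAP Section 3).** Rate 0.20 in each group, margin 0.15, power 0.90, "a one-sided significance level of 0.0125 were used in the calculation of sample size", and "a z-test for a non-inferiority test of two proportions, an allocation ratio of 1:1". Randomised: 444, allowing 10% for loss to follow-up and 10% for statin intolerance.

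**Assumptions.** The share f of baseline non-users in the analysed set is not in the documents; 0% to 10% is shown. It is taken as equal in both arms, with every non-user scored 'yes'. The analysed number is 200 per arm: 444 × 0.90 = 399.6, because early terminators stay in the set, scored 'yes'.

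**1. The plan's own figure.** n per arm = (2.2414 + 1.2816)² × 2 × 0.20 × 0.80 / 0.15² = 12.41 × 0.32 / 0.0225 = 176.5, so 177 per arm and 354 in total. All eight cells of SAP Table 3-2 reproduce. 354 / 0.80 = 442.5, consistent with 444. The sample-size arithmetic is sound; the gap lies in the population definition.

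**2. Observed rates with non-users.** If the rate among users is p, the observed rate is f + (1 − f)p. A true difference of 0.15 among users then appears as (1 − f) × 0.15.

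**3. Probability of declaring non-inferiority.** Φ((0.15 − d)/SE − 2.2414), where d is the difference in observed rates and SE is unpooled.

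For f = 5%, with users at the margin (0.20 and 0.35):
- Observed rates: 0.05 + 0.95 × 0.20 = 0.240 and 0.05 + 0.95 × 0.35 = 0.3825, so d = 0.1425.
- SE = √[(0.240 × 0.760 + 0.3825 × 0.6175)/200] = 0.0457.
- Φ(0.0075/0.0457 − 2.2414) = Φ(−2.077) = 0.0189.

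For f = 5%, with equal rates of 0.20 among users:
- Both observed rates are 0.240, and SE = √(2 × 0.240 × 0.760/200) = 0.0427.
- Power = Φ(0.15/0.0427 − 2.2414) = 0.898.

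| Non-users f | Number in 400 | Observed d | Type I error (simulated) | Power, current set | Power, users only |
|---|---|---|---|---|---|
| 0% | 0 | 0.150 | 0.0125 (0.0126) | 0.934 | 0.934 |
| 2% | 8 | 0.147 | 0.0148 (0.0149) | 0.920 | 0.929 |
| 5% | 20 | 0.1425 | 0.0189 (0.0191) | 0.898 | 0.921 |
| 10% | 40 | 0.135 | 0.0272 (0.0264) | 0.864 | 0.906 |

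Simulation used 1,000,000 trials per scenario. In the users-only column, n per arm is 200(1 − f), that is 196, 190 and 180, and the type I error stays at 0.0125 for every f. With the current set, the 0.15 margin tolerates a difference among users of 0.15/(1 − f): 0.153, 0.158 and 0.167.

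**The case against.** **Eligibility should leave few non-users.** Inclusion criterion 7 requires maximally tolerated statin therapy, and Protocol 3 and 4.1.1 expect participants to be on a statin unless intolerant. Removing intolerant participants therefore removes the designed source of non-users. This stands and limits the size: 10% would mean 40 people, close to the whole intolerance allowance (about 44 of 444). It does not close the gap. The FAS is everyone randomised, including eligibility deviations, and the investigator judges what is maximally tolerated.

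**The 'None' subgroup.** A reader might infer that the SAP expects non-users in this analysis. The documents do not support that. The list is shared with the LDL-C analyses, where intolerant participants remain, and a category with fewer than 10 participants in total is not presented.

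**Scoring of non-users.** A reader might take every non-user to be a certain discontinuer. Under SAP 2.5.1, a baseline non-user who starts a statin and takes it on or after the assessment date is scored 'no'.

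**Equal counts in both arms are assumed.** The observed difference is (1 − f) × 0.15 plus f times the difference among non-users. If the 'yes' rate among non-users were 15 points higher with inclisiran-first, for example because usual-care physicians start statins more often, the dilution would vanish; a larger gap would reverse it. Chance imbalance also matters. With 6% non-users in the inclisiran-first arm and 4% in usual care, a spurious difference of 0.016 appears and power is 0.815; with the shares swapped it is 0.950.

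**The error rate is measured against a users-only target.** For the population as the SAP words it, the nominal level holds. But the stated objective is the stopping of background statin treatment, which presupposes a statin.

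**Existing analyses help in part.** The Per-Protocol Set and the High and Moderate-or-Low subgroups come closer to users only. Neither is the primary test. The one sensitivity analysis for this variable (SAP 2.5.5) deals with a mismatch between randomisation and CRF entries.

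**Intolerant participants who take a statin.** A reader might infer that excluding them is an error to be reversed in the primary analysis. Both documents choose a population without intolerance, and the sample size allows 10% for it. Putting these participants back would change the estimand. How many of the roughly 44 take a statin is not stated.

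**Conclusion.** The gap in the definition is real: nothing in the analysis set or the derivation requires a statin at baseline, and a non-user who never starts one counts as a discontinuer in a co-primary non-inferiority test. Its effect is conditional. With equal shares in both arms, 200 per arm and 0.20 against 0.35 among users, the one-sided type I error is about 0.015, 0.019 and 0.027 at 2%, 5% and 10% non-users, against 0.0125. Under equality, power falls from 0.934 to 0.920, 0.898 and 0.864. The lower end of the range is the more plausible, given eligibility. The documents do not establish that the error rate is inflated in this trial, because the share of non-users and its split by arm are unknown. The correction is still worth making, since it removes the dependence on that share.

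**What to change.** In SAP 2.5.2 and the estimand 2 population, restrict the primary analysis of variable 2 to FAS participants without statin intolerance who have a statin ongoing on study Day 1 (baseline intensity low, moderate or high). In addition:

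- Keep the current set as a sensitivity analysis.
- State in SAP 2.5.1 how a participant with no statin record is coded in that analysis.
- Drop the 'None' intensity subgroup for this endpoint.
- As a further sensitivity analysis only, add participants with an intolerance history who take a statin at baseline.
- List the change in SAP Section 4, because it narrows the population in Protocol 12.4.2.

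The cost is SAP wording and one flag; baseline statin intensity is already derived for SAP 2.4.2 and 2.6.1. The restriction uses a baseline characteristic, so the comparison remains randomised. The analysed set becomes slightly smaller (190 per arm at 5% non-users). Under the assumptions above, power is nevertheless higher than with the current set, 0.921 against 0.898.

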2.5.3 Handling of intercurrent events

The remaining intercurrent events of the primary estimand for the two primary efficacy variables are the following:

1. Potential use of inclisiran by participants in the usual care group. This intercurrent event will be ignored in the analysis, as the design of the trial allows for participants in the usual care group to potentially use inclisiran.
2. Discontinuation of study treatment (in inclisiran participants). This intercurrent event will be ignored in the analysis.

2.5.4 Handling of missing values not related to intercurrent event

For the primary analysis of primary efficacy variable 1, the MMRM implicitly imputes missing data under a missing at random assumption.

For the primary analysis of primary efficacy variable 2, participants for whom it cannot be ascertained that they are on statin therapy at the end of study will be assumed to have discontinued statin therapy (discontinued statin = 'yes').

2.5.5 Sensitivity analyses

The sensitivity analysis of primary efficacy variable 1 to address the primary objective will be based on the following estimand:

- Population: Defined through appropriate inclusion/exclusion criteria to reflect the targeted population
- Variable: Percent change from baseline in LDL-C [The primary analysis time point is at Day 330.]
- Treatment: "Inclisiran first" implementation strategy or usual care
- Remaining intercurrent events: 1. Potential use of inclisiran by participants in the usual care group. This intercurrent event will be ignored in the analysis, as the design of the trial allows for participants in the usual care group to potentially use inclisiran. 2. Discontinuation of study treatment (in inclisiran participants). This intercurrent event will be ignored in the analysis.
- Summary measure: Probability of observing the same or a more favorable response with "inclisiran first" implementation strategy relative to usual care

For the above estimand, primary efficacy variable 1 will be analyzed at each time point for the Full Analysis Set using the van Elteren test, adjusting for [REDACTED] (Stokes et al 2012).

The probability of observing the same or a more favorable response (θ_0) with "inclisiran first" implementation strategy relative to usual care will be estimated using nonparametric methods, and the associated 97.5% confidence interval will also be reported (Chen and Kianifard 2000).

For both primary efficacy variable 1 and primary efficacy variable 2, an additional sensitivity analysis will be performed where participants for whom [REDACTED] entered at

randomization (via Interactive Response Technology (IRT)) did not match [REDACTED] entered at baseline (via CRF) were excluded from the analysis.

2.5.6 Supplementary analyses

A supplementary analysis of primary efficacy variable 1 will be based on the following estimand:

- Population: Defined through appropriate inclusion/exclusion criteria to reflect the targeted population
- Variable: Percent change from baseline in LDL-C [The primary analysis time point is at Day 330.]
- Treatment: "Inclisiran first" implementation strategy or usual care
- Remaining intercurrent events: 1. Potential use of inclisiran by participants in the usual care group. 2. Discontinuation of study treatment (in inclisiran participants). Data after the occurrence of either one of the above two intercurrent events will be excluded from the analysis (using MMRM).
- Summary measure: Least-squares mean difference between "inclisiran first" implementation strategy and usual care

2.6 Analysis supporting secondary objectives

The secondary objectives include the following:

- To assess the absolute change in LDL-C of an "inclisiran first" implementation strategy compared to usual care at Day 330, as well as average of percent and absolute changes in LDL-C levels to each post-baseline visit
- To assess the proportion of participants reaching pre-specified LDL-C targets among those receiving an "inclisiran first" implementation strategy compared to usual care at Day 330
- To assess plasma lipids, lipoproteins and triglycerides in participants receiving an "inclisiran first" implementation strategy compared to usual care at Day 330
- To assess changes in and adherence to background lipid-lowering therapy in participants receiving an "inclisiran first" implementation strategy compared to usual care at Day 330
- To assess visit-to-visit LDL-C variability from Day 90 until Day 330
- To assess overall safety and tolerability of inclisiran

